### 7.1. Primary Objective

Evaluation of the efficacy of RDV in reducing 14-day mortality in newly diagnosed, hospitalised, non-ventilated severe COVID-19 patients.

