### 8.2. Treatments studied

The key treatment of interest is RDV, given to patients at the early stage of a COVID-19 infection who have a high probability of developing severe disease. Guidelines were in place for its use in the UK – it was recommended for newly hospitalised patients, no later than within 10 days of symptom onset, and only initiated in non-ventilated patients. Patients were recommended to receive 200mg on Day 1 of treatment, followed by 100mg daily for 4 days. An optional additional 5 days of 100mg daily was recommended till 29th September, but the wording changed over time:

26th May to 2nd June: “If a patient does not demonstrate clinical improvement”

3rd June to 28th September: “If a patient deteriorates and progresses to ventilation and/or ECMO treatment”

29th September onwards: “Ensure that clinicians prescribe a maximum treatment course of 5 days” – this was due to a disruption in supply of the drug. It is stated that some exceptions may receive additional doses, but these were undefined by the guidelines.

The comparison treatment is: Standard of care, without RDV.

NB: Standard of care evolved as knowledge of the disease and how to treat it evolved. Co-medication with the corticosteroids dexamethasone and hydrocortisone became recommended for some patients part-way through our study period – these are not expected to interact with RDV, and so we expect that RDV patients will have received these in the same way as non-RDV patients. The drugs Hydroxychloroquine and Chloroquine phosphate were not recommended as concomitant medications for RDV from 3rd September 2020.

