### 8.3. Baseline: definition

We take a common baseline to be ‘date of hospitalisation due to COVID’. It is important to note that this is not necessarily when RDV was initiated, though it is likely that it was administered soon after admission. The definition of baseline depends on the where the infection was acquired:

Community acquired COVID-19 i.e. admitted with symptoms consistent with COVID-19:

Baseline = Date of admission to hospital

For hospital acquired COVID-19 :

Baseline = Date positive COVID-19 test was collected

‘Hospital acquired’ is defined as: symptom onset at least 5 days after hospital admission.

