#### 8.4. Patient population studied

Inclusion/exclusion guidelines for RDV use changed slightly over time. The following criteria are designed to create a cohort of patients that would have been eligible to receive RDV from baseline. They apply for the whole study period, and will be used to define our analysis cohort:

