### 8.7. Definition of treatment groups

The analysis cohort will be split into two treatment groups: RDV and non-RDV. As the study is observational, allocation of treatment is decided by clinicians.

A matching process will be carried out to link RDV patients with non-RDV patients as follows:

A logistic regression with dependent variable RDV (Yes/No) will be fitted including the following covariates:

1. Month of baseline
2. Tier of participating centre (0 / 1 and 2)
3. Sex
4. Age
5. Broad ethnicity group (White / Asian / Black / Other)
6. Clinically extremely vulnerable status (Yes: Cancer / Yes: Severe respiratory condition / Yes: on immunosuppression therapy / Yes: Other / No)
7. Comorbidities: Diabetes (Y/N), Hypertension (Y/N), Obesity (Y/N), Chronic Cardiac disease (Y/N), CPD (Y/N), Asthma (Y/N)
8. Where COVID was acquired (Community / Hospital)
9. Admitted to HDU/ICU at baseline (Y/N)

Note: a pragmatic approach will be taken – the list above defines a best-case set of matching criteria; it may be necessary for categories to be collapsed to simplified discriminators (e.g. White vs Other ethnicity, or ‘Total number of comorbidities’), should the model become over-parametrised. If possible, 2nd order interactions will be investigated, and if statistically significant, added to the model. All main effects will be retained in the model, even if not significant.

The fitted model will be used to calculate the probability of receiving RDV for each patient according to their baseline factors. The probability calculated is called their propensity score (PS). Boxplots will

be presented showing the distribution of PS in each treatment group. Patients who were given RDV will then be matched to a control patient / patients with a similar PS who did not get RDV, using a nearest neighbour matching algorithm and a pre-specified maximum difference in PS (calliper width) of 0.2 standard deviations. The ratio of RDV patients to controls may be 1:1 or higher – to a maximum of 1:4 (Rassen (2012) suggests that 1:n matching leads to higher precision in estimating effect sizes, with a cost of a small increase in bias with increasing n). Controls are chosen without replacement, so may not be matched to more than one RDV patient.

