### 9.2. Secondary Outcomes

Secondary outcomes are:

1. Time-to-recovery, where recovery is defined as: discharge from hospital or continued hospitalisation with no on-going health-care needs related to COVID-19
2. 28-day mortality
3. Time-to-death
4. Clinical status at day 15e
5. Length of time receiving supplementary oxygen
6. Time-to-first ventilation
7. Use of non-invasive ventilation at any time during 28 days post baseline
8. Use of mechanical ventilation / ECMO at any time during 28 days post baseline
9. Acute renal injury/acute renal failure at any time during 28 days post baseline
10. Liver dysfunction at any time during 28 days post baseline

Note: length of hospital stay was a key outcome of the SOLIDARITY trial, but is not listed as an outcome here. This is because our cohort includes hospital acquired COVID patients, and some patients with long-term institutionalisation. We are more interested in COVID-related hospital stay, but data on this are not collected beyond 28 days, and so we use the outcome ‘Time-to-recovery’ to double as inference to test whether RDV impacts on short-term length of stay.

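### Hospital-acquired cases sit awkwardly with the stated RDV-eligibility aim, and length of prior hospital stay is not controlled among them

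*SAP*

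**What the plan says.** SAP 8.2 describes the UK recommendation for RDV: "it was recommended for newly hospitalised patients, no later than within 10 days of symptom onset, and only initiated in non-ventilated patients". SAP 8.4 says the inclusion and exclusion criteria are "designed to create a cohort of patients that would have been eligible to receive RDV from baseline". The lists in 8.4.1 and 8.4.2 enforce the non-ventilated condition. They set no limit on time already spent in hospital.

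SAP 8.3 gives hospital-acquired cases their own day 0: "Baseline = Date positive COVID-19 test was collected". It defines them by "symptom onset at least 5 days after hospital admission", with no upper bound. SAP 9.2 states that "our cohort includes hospital acquired COVID patients, and some patients with long-term institutionalisation", and gives this as the reason for not using length of stay as an outcome. The primary objective (7.1) names its target as "newly diagnosed, hospitalised, non-ventilated severe COVID-19 patients".

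Place of acquisition enters the propensity model in 8.7 as a two-level item, alongside calendar month, centre tier, sex, age, ethnicity, extreme-vulnerability status, six comorbidities and HDU/ICU admission. The risk-score balance check in 8.7 and the primary outcome model in 17.2.1 both use age, sex and comorbidity count.

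**The concern.** There are two linked problems.

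The first is wording. Read together, 8.2 and 8.4 suggest a cohort of new admissions, while 8.3 and 9.2 describe one that also holds established inpatients. A reader cannot tell whether the authors regard hospital-acquired cases as meeting the 8.4 aim.

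The second is confounding. Time from admission to baseline is zero for community cases, because admission is their baseline. For hospital-acquired cases it can be a few days or much longer. Longer-stay patients may have been offered RDV less often, and their 14-day mortality may partly reflect the illness that kept them in hospital. If both hold, untreated hospital-acquired patients would carry more risk than treated ones even after the community/hospital split is balanced. The primary odds ratio would then lean towards RDV. Days from admission to baseline appear in no propensity model, balance check, outcome model or baseline table (17.1 lists days since symptom onset). No analysis restricted to community-acquired cases is planned, although Section 19 does treat the early-ventilated group separately.

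**Working it through.** **The plan's own figure.** SAP 17.2.1 takes 14-day mortality of 3.1% and 500 RDV patients: 500 × 0.031 = 15.5, rounded to 16 deaths, and 2 × 16 = 32 under 1:1 matching. Both reproduce.

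**Inputs.** From the SAP: m = 3.1% (17.2.1); nearest-neighbour matching without replacement, calliper 0.2 SD, 1:1 to 1:4 (8.7). Everything else is assumed, because the SAP gives no hospital-acquired share, RDV uptake or mortality for this group.

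**Closed form, no RDV effect.** Let the hospital-acquired share h be equal in both matched groups. Let s be the long-stay fraction among hospital-acquired cases, and k the mortality ratio of long-stay patients to everyone else. Then group mortality is

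p = m × [1 + h × s × (k − 1)], and OR = [pT/(1 − pT)] / [pC/(1 − pC)].

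Example with h = 10%, k = 3, s = 10% in RDV and 50% in controls:
- pT = 0.031 × (1 + 0.1 × 0.1 × 2) = 0.03162
- pC = 0.031 × (1 + 0.1 × 0.5 × 2) = 0.03410
- OR = (0.03162/0.96838) / (0.03410/0.96590) = 0.925

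The gap is 0.00248, or about 1.2 deaths per 500 patients.

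| h | k = 1 | k = 2 | k = 3 | k = 4 |
|---|---|---|---|---|
| 5% | 1.00 | 0.980 | 0.961 | 0.942 |
| 10% | 1.00 | 0.961 | 0.925 | 0.892 |
| 20% | 1.00 | 0.925 | 0.862 | 0.809 |

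With s = 30% against 70%, no cell moves by more than 0.016.

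**Simulation of the matching.** The base case was a cohort of 20,000 with 15% hospital-acquired, half of them long-stay. RDV uptake was 12% in community cases, 6% in short-stay and 1% in long-stay hospital cases. Long-stay mortality was three-fold and RDV had no effect. The propensity score used age and the two-level term, and the outcome model was age-adjusted logistic regression; 60 runs per scenario.
- The two-level term does its job: hospital-acquired share 5.0% (RDV) against 5.1% (controls). Without it the shares were 4.9% and 16.2%, and the OR was 0.86.
- It does not balance prior stay: long-stay share 0.7% against 2.6%. The ORs were 0.985 (1:1) and 0.947 (1:4). By hand, (1 + 2 × 0.007)/(1 + 2 × 0.026) = 1.014/1.052 = 0.964, so those two values differ mainly by noise.
- Uptake 12% in short-stay and 3% in long-stay cases: 0.98. Uptake 5% in community and short-stay cases and 1% in long-stay: 0.93.
- 30% hospital-acquired in the source cohort and four-fold mortality: 0.86.
- Uptake of 1% in all hospital-acquired cases: 1.4% of each matched group is hospital-acquired, OR 1.00. Even if the treated ones were all short-stay and half the controls long-stay, the risk ratio would be 1/(1 + 0.014 × 0.5 × 2) = 0.986 at k = 3.
- Controls on the method: no long-stay excess mortality gave 0.99, and equal uptake within hospital-acquired cases gave 0.98. Noise is therefore a few hundredths.

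**The case against.** Including these patients is a declared choice, not an oversight. They satisfy the objective's wording (newly diagnosed, in hospital), have their own baseline rule, enter the propensity model, are tabulated in 17.1, and are the stated reason for dropping length of stay. The phrase in 8.2 summarises guidance that the SAP does not reproduce, and nowhere does the SAP say that hospital-acquired cases were ineligible. A reader might infer that controls fall outside the recommendation. The text shows a tension to reconcile, not a breach. This stands.

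The two-level term is also not the only protection. Age, vulnerability status, comorbidities and HDU/ICU admission all bear on frailty, and the outcome model ideally adjusts again for age and comorbidity count. Only what prior stay adds beyond these can bias the result. This stands too. The calculations above include age at most, so they tend to overstate what would be left.

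The mechanism also limits itself. The more closely clinicians kept RDV to new admissions, the fewer hospital-acquired controls are matched.

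Finally, the effect is small beside sampling error. With 3.1% mortality in 500 RDV patients and 2,000 controls, SE(log OR) = √(1/15.5 + 1/484.5 + 1/62 + 1/1938) = 0.29, so the 95% interval around an OR of 1 is about 0.57 to 1.76. That is fair at this size, but Section 10 sets no upper limit on numbers, and bias does not shrink as the sample grows.

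What the objection leaves untouched is that prior stay is measured nowhere in the analysis, so the plan could not show whether a difference exists.

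**Conclusion.** The point holds as a cheap improvement. The wording of 8.2 and 8.4 needs reconciling with 8.3 and 9.2, and a possible confounder available from dates already in use is neither balanced, checked nor adjusted for.

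Under assumed inputs and no RDV effect, the OR is mostly about 0.93 to 1.00. In the table it falls below that only at a 10% share with four-fold mortality, or a 20% share with at least three-fold. It is about 1.00 if few hospital-acquired patients received RDV or if long-stay patients have no excess mortality.

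Three stronger readings are tempting and not supported:
- **That the plan biases 14-day mortality towards RDV.** This direction needs both lower uptake and higher residual mortality with longer prior stay. It is plausible, but the SAP gives no evidence for either.
- **That the bias is large.** Assuming 10% against 25% mortality among hospital-acquired cases at a 10% share gives 0.0379 against 0.0529, an OR of 0.71. Neither rate has a source, and the calculation supposes that the contrast survives matching and adjustment intact.
- **That the main analysis must drop hospital-acquired cases.** That would change the declared target population. It is a trade-off, not a correction.

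**What to change.** 1. In 8.4, state whether hospital-acquired cases are regarded as meeting the eligibility aim, and bring 8.2, 8.3 and 9.2 into line. Keep the declared population.
2. In 8.7, add days from admission to baseline to the propensity model (0 for community cases), beside the existing place-of-acquisition term.
3. In 17.1, add the same variable to the baseline table for the full and matched cohorts by treatment group, so that any remaining difference is visible.
4. Prespecify a sensitivity analysis of 14-day mortality restricted to community-acquired cases.

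The cost is SAP wording and minor programming. The dates are already needed to apply 8.3, so there is no new data collection and little or no added missingness in the propensity score. The downsides are one more propensity covariate and slightly lower precision in the sensitivity analysis.

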##### 8.4.1. Inclusion criteria

- Laboratory confirmed SARS-CoV-2 infection
- Hospitalised
- Aged  $\geq 18$  yearsa at baseline
- Requiring supplementary oxygen ( $SpO_2 \leq 94\%$ ) at any time during 24 hours post baseline
- RDV initiated  $\leq 24$  hours post baseline (RDV group only)b

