##### 8.4.2. Exclusion criteria

- Requiring a high flow cannula, any ventilation or ECMO during first 24 hours post baselinec
- Pregnant
- Chronic kidney disease
- RDV initiated  $> 24$  hours post baselined
- Is a COVID-19 re-admission (was previously hospitalised for COVID-19)
- Missing Day 1 Daily Treatment CRF
- Missing ‘Medication’ section of the Outcome CRF

---

a RDV was recommended in people aged 12 and over, and weighing over 40kg. Weight was not generally measured at baseline for practical reasons, so we have excluded children aged 12-17 in order to be sure that no-one in the control group was likely to weigh less than 40kg.

b This criteria is an ideal, to measure the effectiveness of RDV initiated close to baseline. If RDV is more routinely given later than this, we will either remove this criteria, or move the window of inclusion to say 3 days. Statistics describing when RDV treatment was initiated compared with baseline, will be presented.

c This subgroup will be analysed separately (see Section 19).

d See footnote b above.

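### Laboratory confirmation has no time limit, so a patient first positive days after admission is a control if untreated but is excluded if RDV follows that positive

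*SAP*

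**What the plan says.** Section 8.4 states that the criteria are "designed to create a cohort of patients that would have been eligible to receive RDV from baseline". Section 8.4.1 then lists "Laboratory confirmed SARS-CoV-2 infection" with no date or window, although the oxygen criterion and the RDV start beside it are both tied to the first 24 hours.

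Section 8.3 fixes baseline in two ways. For community-acquired disease, meaning "admitted with symptoms consistent with COVID-19", it is "Baseline = Date of admission to hospital". For hospital-acquired disease it is "Baseline = Date positive COVID-19 test was collected". The hospital-acquired class is defined by "symptom onset at least 5 days after hospital admission", so symptoms decide the class and the test date does not.

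Section 8.4.2 excludes "RDV initiated $> 24$ hours post baseline". Footnotes b and d make that rule provisional: if RDV was usually given later, "we will either remove this criteria, or move the window of inclusion to say 3 days". Neither footnote puts a date on the test.

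**The concern.** A cohort meant to be eligible for RDV from baseline should be defined by what was true at baseline or within the common 24-hour window. Here one criterion can be met at any later time, and what happens after it is met decides whether the patient stays. Untreated patients stay and count from admission. Patients whose treatment waited for the late positive are removed. The control group therefore holds late-confirmed patients selected on their later course, with no corresponding route into the RDV group for those whose treatment waited.

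The primary outcome is death by day 14 counted from baseline, so selection on events in the first days acts directly on the primary odds ratio.

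**Working it through.** **Tracing one patient.** Take a patient admitted with symptoms, on oxygen within 24 hours, not ventilated, and first sampled positive on day 4.

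- Section 8.3: symptoms were present at admission, so the case is community-acquired and baseline is admission (day 0).
- Section 8.4.1: the day-4 sample satisfies laboratory confirmation.
- Never given RDV: a control, followed from day 0.
- Given RDV on day 4 or later: excluded by section 8.4.2.

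**Does anything later correct this?** The nine covariate items in section 8.7 contain no test date or time to confirmation. Month of baseline and centre tier might reflect testing speed in general, but not an individual's delay. The balance check in section 8.7 and the primary model in section 17.2.1 use only sex, age and number of comorbidities. The fallback in section 8.1, comparison with all eligible patients, uses the same criteria.

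**Illustrating the size.** The SAP gives no figure on this point. The only input taken from it is 14-day mortality p = 0.031 (section 17.2.1). Its use there reproduces: 500 × 0.031 = 15.5, rounded to 16 deaths, and 2 × 16 = 32. The rest is assumed:

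- f = 0.20: share confirmed late among otherwise eligible patients not started on RDV within 24 hours, before any removals
- d = 3 days from admission to the positive sample
- q = 0.25 or 0.50: share of late-confirmed patients alive at day d who are then treated, and so excluded
- s: share of 14-day deaths falling before day d. If deaths are uniform, s = 3/14 = 0.214. If front-loaded (exponential of scale 6 days truncated at 14, mean 4.5 days), s = (1 − e^(−3/6))/(1 − e^(−14/6)) = 0.3935/0.9030 = 0.436.
- no drug effect, so the RDV odds are 0.031/0.969 = 0.03199

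Control risk = [(1 − f)p + f·N] / [(1 − f) + f·M], where N is deaths and M is patients kept, per late-confirmed patient.

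- Case A, patients dying before day d are still confirmed and enter: N = ps + (1 − q)p(1 − s), M = ps + (1 − q)(1 − ps).
- Case B, they are never confirmed and never enter: N = (1 − q)p(1 − s), M = (1 − q)(1 − ps).

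Worked example (A, front-loaded, q = 0.50): N = 0.02225 and M = 0.50675. Control risk = (0.0248 + 0.00445)/(0.8 + 0.10135) = 0.03245, odds 0.03354, OR = 0.03199/0.03354 = 0.954.

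| Timing of deaths | q | A: control risk | A: null OR | B: control risk | B: null OR |
|---|---|---|---|---|---|
| Uniform | 0.25 | 3.13% | 0.989 | 3.00% | 1.035 |
| Uniform | 0.50 | 3.17% | 0.977 | 3.03% | 1.024 |
| Front-loaded | 0.25 | 3.17% | 0.978 | 2.89% | 1.074 |
| Front-loaded | 0.50 | 3.25% | 0.954 | 2.95% | 1.051 |

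Case A gives 0.95–0.99 and case B gives 1.02–1.07.

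**Sensitivity.** With a constant hazard, f = 10–20%, d = 2, 3 or 5 days, and 14-day mortality of 3.1% or an assumed 10%, the ranges are 0.96–1.00 (A) and 1.01–1.06 (B). If instead late-confirmed patients make up 20% of the controls that remain after removals, the risk is 0.8p + 0.2·N/M. The ranges then widen to 0.92–0.99 (A; extreme 0.8 × 0.031 + 0.2 × 0.0439 = 0.0336, OR 0.921) and 1.05–1.10 (B; extreme 0.8 × 0.031 + 0.2 × 0.0177 = 0.0283, OR 1.097).

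**Against sampling error.** With 500 per group and 16 deaths in each, the standard error of the log OR is √(2/16 + 2/484) = 0.359, and the 95% limits lie a factor e^(1.96 × 0.359) = 2.02 either side. These distortions are small beside that, but they do not shrink as the cohort grows.

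**The case against.** The strongest reply is that the gap is real but its effect is not established. Four parts of it stand.

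- **Direction.** A reader might infer that late-confirmed controls have guaranteed survival up to the positive sample, so that the bias runs against RDV. That needs every patient dying before the usual confirmation day to go unconfirmed. Section 8.4.1 does not say so, and a criterion without a time limit could be met by a sample taken or reported after death. Those deaths then stay in while treated survivors are removed, and the bias favours RDV.
- **Size.** Larger figures need stacked assumptions. A null OR near 1.24 takes 30% of controls late, a 5-day delay, front-loaded deaths, loss of every early death and no removal of treated patients (0.7 × 0.031 + 0.3 × 0.0118 = 0.0253; OR 1.235). The SAP supports none of these values. The cohort needs oxygen within 24 hours and largely presents with symptoms, so late first positives may be few.
- **Who is affected.** A reader might also infer that late-confirmed patients can occur only among controls. The guideline summary in section 8.2 does not say that RDV had to await a positive result. A patient treated on suspicion within 24 hours and confirmed later would enter the RDV group.
- **A provisional rule.** Footnotes b and d may relax the 24-hour exclusion. A 3-day window would still exclude later starts. Removing the rule would end this asymmetry, but would admit late-treated patients with follow-up counted from before treatment.

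What the reply does not answer is the contradiction with section 8.4: the criteria as written admit patients who did not yet meet the confirmation criterion in the window used to define treatment, and keep them according to what happened later.

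**Conclusion.** The point holds as an eligibility fault that should be corrected before analysis. It follows from sections 8.3, 8.4.1 and 8.4.2 read together, conflicts with the stated aim in section 8.4, and is not corrected by matching, the balance check or adjustment.

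Its effect on the primary odds ratio cannot be signed or sized from the SAP. The illustrative ranges (about 0.95–0.99 or 1.02–1.07, depending on whether early deaths enter) rest on assumed values for the late share, the delay, the timing of deaths and the share treated late. They show a modest distortion that can go either way. They do not support a claim that the result will be biased against RDV, or in its favour.

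**What to change.** In section 8.4.1, require for both groups a positive SARS-CoV-2 sample collected no later than 24 hours after baseline; a positive shortly before admission also qualifies. If footnote b widens the RDV window, widen this limit to match. If the 24-hour rule is removed altogether, state the confirmation limit explicitly. Section 8.3 works in dates, so say how 24 hours translates into calendar days.

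Report by group the time from baseline to positive sample, the number removed by the limit and the number with no test date. Repeat the primary analysis without the limit as a sensitivity analysis.

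The cost is one line of text, a filter and one extra run, with three drawbacks. Late-confirmed patients are lost from either group, including any RDV patients started on suspicion. Patients with a missing test date are also lost; section 8.3 uses that date only for hospital-acquired cases, so its completeness for community cases needs checking first. Finally, the filter works on collection date, so it does not address a patient sampled at baseline whose result came back late: that patient is still a control if untreated and still excluded if treated after the result.
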